1. LAY SUMMARY

1.1 Background

During sleep, many people have times when they breathe shallowly or completely stop. If a person stops breathing for more than 10 seconds, this is called an 'apnoea'. If shallow breathing, where the airflow drops by 30% or more, lasts for more than 10 seconds and results in the oxygen level in the person's blood decreasing by 3% or more, it is called a 'hypopnoea'. If a person has these events frequently, it disrupts their sleep and they do not awake refreshed. The tiredness can be so significant that it affects their life and can lead to accidents. These breathing events can also put strain on the heart, leading to cardiovascular conditions. These sleep disorders, usually called 'Sleep Apnoea', and can be treated for most people using 'continuous positive airways pressure', CPAP.

1.2 Why is this study important?

Sleep Apnoea diagnosis currently takes place at a specialist clinic, primarily because the diagnostic devices are complicated to use and interpret, as well as expensive. The standard tests, which patients wear overnight, do not measure actual breathing but rely on a series of other measurements which indicate that the person has stopped or reduced their breathing.

1.3 What is the test?

The new test is very simple. It just requires the user to wear a mask, similar to ones used for CPAP treatment, overnight and then return the mask for data analysis. The mask contains a small sensor to measure changing pressures in the user's breathing during the night, which records when the user has an apnoea or a hypopnea.

1.4 How does the device work?

Over the past two years, a newly formed company, Apnea-Tech Limited, has developed a simple, low-cost device to assist medical professionals in screening for sleep apnoea and hypopnea. It has been awarded taxpayer funding through Innovate UK to develop its novel device. The screener, called Apne-Scan, uses a mask fitted with a pressure sensor to monitor actual breathing.

1.5 The Key Question

Can the simple, low-cost screener assist a clinician in diagnosing sleep apnoea as well as the more expensive standard sleep apnoea test?

1.6 How are we going to answer this question?

In this study, patients will be invited to take part if they have been referred by a clinician to the sleep clinic for a standard diagnostic test. Participation in the study does not change their NHS care pathway for their condition but could eventually lead to others being screened earlier, reducing NHS costs. If they agree to take part, at the same time as the standard test, participants will wear an Apne-Scan mask to capture details of their actual breathing. They will also complete a short questionnaire answering questions about their age, sex, weight, measurements and about using the mask. Having worn Apne-Scan overnight, they will return the device to the sleep clinic, with the standard test, for data analysis by Apnea-Tech. Apnea-Tech will not receive any personal information about the user. The company will only receive their study participant number, the data captured by their Apne-Scan device, the participant's oxygen saturation level data captured by the standard test and the participant's questionnaire answers.

1.7 What is the potential public health impact of this study?

Independent research indicates that treating Sleep Apnoea reduces overall NHS costs. It also suggests that, in the U.K. alone, better diagnosis of Sleep Apnoea could lead to a reduction of up to 40,000 fatigue-related accidents per year.

1.8 How will this research be used?

The results from analysing the data from the Apne-Scan device will be compared with those from the standard test to establish the comparability of the two methods. The study results will be published in either a journal or at a conference. Apnea-Tech will also use the results to develop a data analysis program to assist clinicians in diagnosing sleep apnoeas and hypopneas.

1.10 The 'Apne-Scan' screening device

Figs 1, 2 and 3: The Apne-Scan device (close up), being worn (front) and being worn (side)

2. ABBREVIATIONS

ADE	Adverse Device Effect
AE	Adverse Event
ASADE	Anticipated Serious Adverse Device Effect
CE	EU Conformity Assessed
CI	Chief Investigator
CSA	Central Sleep Apnoea
DMC	Data Management Committee
DUID	Device User ID
EHR	Electronic Healthcare Record
GCP	Good clinical practice
GDPR	General Data Protection Regulations
GP	General Practice / General Practitioner
HCP	Healthcare professional
HYP	Hypopnea
IHE	Indicative Hypopnea Event
IFU	Instructions For Use
MHRA	Medicines and Healthcare products Regulatory Agency
NHS	National Health Service
OSA	Obstructive Sleep Apnoea
PI	Principal Investigator
PIS	Participant Information Sheet
R&D	Research and Development
REC	Research Ethics Committee
SA	Sleep Apnoea (CSA, OSA and HYP)
SADE	Serious Adverse Device Effect
SAE	Serious Adverse Effect
SPO2	Oxygen saturation level in the blood
TSC	Trial Steering Committee
USADE	Unanticipated Serious Adverse Device Effect
UKCA	UK Conformity Assessed

3. SYNOPSIS

STUDY TITLE	An exploratory study of a novel, low-cost sleep apnoea screening device to compare its capability to identify apnoeas and hypopneas with current standard sleep apnoea test devices.
INTERNAL REF. NO.	G001-23
PROBLEM STATEMENT	
Sleep apnoea (SA) has been estimated to affect nearly 1 billion people worldwide ^(Reference 1) but only 15-20% of people with the condition are diagnosed and treated. It is estimated that about 20% of the people with SA have Central Sleep Apnoea (CSA) and the remaining 80% have Obstructive Sleep Apnoea (OSA).
 
Cost effective treatments for OSA exist, e.g., CPAP, which have a significantly beneficial effect on the patient, reduce tiredness and the onset of co-morbidities⁴⁻⁶.
 
Current diagnostic aids are expensive, tend not to monitor the user's actual breath pathway, are complicated for the user and time consuming for the clinical team to interpret. An easier to use, low cost device could streamline the diagnostic pathway and release capacity in the sleep clinic for treatment.

PRIMARY HYPOTHESIS	Use of Apne-Scan DC1 to screen patients for possible sleep apnoea supports the clinician in reaching a diagnosis and identifies people who do not have the symptoms of sleep apnoea.
SECONDARY HYPOTHESES	
Apne-Scan DC1 has the potential to reduce the cost of diagnosis for sleep apnoea.
 
Apne-Scan DC1 is easy-to-use for both clinicians and patients.
 
Apne-Scan DC1 has the potential to reduce patient visits to the Sleep Clinic and hence reduce the hospital's CO₂ footprint.

SAFETY HYPOTHESIS	Apne-Scan DC1 does not indicate that users with moderate or severe sleep apnoea or hypopnea do not have the conditions.
STUDY DESIGN	Simple comparative
STUDY PERIOD	One night per participant
STUDY PARTICIPANTS	
Inclusion criteria
 
The study participants must:
 
 • Have been referred by a clinician to the sleep clinic for diagnosis of a sleep disorder, possibly sleep apnoea. • Be about to be screened for possible sleep apnoea using a standard sleep apnoea test device. • Be between the ages of 18 and 75 and have provided informed consent for the study. 
Exclusion criteria
 
People who:
 
 • Have not been referred by a clinician to a sleep clinic for diagnostic tests for sleep disorders other than for possible sleep apnoea. • Cannot tolerate wearing a mask overnight.

	
 • Have a neurological condition, learning or physical difficulties such that they are unable to remove a mask should they become distressed. • Are not capable of understanding the English language version of Apne-Scan DC1's IFU. • Are under the age of 18 years old or over 75 years old. • Are not capable of giving informed consent.
PLANNED SAMPLE SIZE	
The study will recruit 25 participants on initial referral to the sleep clinic for diagnostic tests for possible sleep apnoea.
 
A total of 40 Apne-Scan DC1 devices will be available for use by the clinical team and study participants.

PRIMARY OBJECTIVE	
The primary objective of this exploratory study is to assess Apnea-Tech's UKCA Class I Apne-Scan DC1 sleep apnoea screening device in assisting a clinical diagnosis of sleep apnoea in comparison to standard sleep apnoea test devices (ResMed NOX T3 and Phillips Alice Night One).

SECONDARY OBJECTIVES	
The secondary objectives of this exploratory study are:
 
To review whether the effectiveness of Apnea-Tech's Apne-Scan DC1 low-cost screener seems to be impacted by the severity of the user's condition determined by a standard sleep apnoea test device as:
 
 • Mild sleep apnoea • Moderate sleep apnoea • Severe sleep apnoea 
To review whether the effectiveness of Apnea-Tech's Apne-Scan DC1 low-cost screener seems to be impacted by the severity of the user's condition determined by a standard sleep apnoea test device as:
 
 • Mild hypopnoea • Moderate hypopnoea • Severe hypopnoea 
To review whether there are artifacts in the Apne-Scan data which can be used to accurately predict the change in the user's SPO2.
 
To assess the usability and effectiveness of the device in capturing the minimum data required for screening for sleep apnoea.

OUTCOMES	
Primary Outcome
 
The primary outcome of interest is the data capture of the changing pressures in the user's breathing, whilst asleep, as recorded by the Apne-Scan DC1 device.
 
Note: The minimum evidence for successful completion of the study is 60 hours of breathing data captured by a minimum of 15 participants.
 
Secondary Outcomes
 
 • An overall comparison of the SA screening output from Apne-Scan DC1 with that from standard sleep apnoea test devices (ResMed NOX T3 and Phillips Alice Night One). • A comparison stratified by the severity of the SA indicated by standard sleep apnoea test devices.

[figure not shown]
- A comparison stratified by the severity of the hypopnoea indicated by standard sleep apnoea test devices.
- A possible first-generation algorithm, based on the Apne-Scan data, to predict the user's SPO2 level.

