10.3.2.3 Device Usage and Data Flow

The Apne-Scan DC1 device is a single user, single use device. It has a single flow sensor which records the pressure in the breath pathway twice per second. The definitions for diagnosing sleep apnoeas and hypopneas are all relative, based on percentage changes in sensor readings. The device will only recognise Indicative Hypopnea Events, because it does not confirm desaturation, unless the captured data can be used to accurately predict the user's SPO2 level at any time. There is no need for any calibration by the clinician or the user.

Once the device has been started, it continues to monitor the pressure in the breath pathway until the battery runs flat, which is targeted at over eight hours. The pressure readings are recorded sequentially on the internal memory for later download. They remain in the memory when the battery has run down.

After use the study participant return the used Apne-Scan DC1 and completed questionnaire, with the standard test, to the sleep clinic. The Apne-Scan data, together with the post-use questionnaire and the standard test's SPO2 level data, will be securely stored by participant number by the company and then analysed for possible apnoeas, indicative hypopneas and prediction artifacts within the Apne-Scan data of changes in SPO2 levels.

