13. DATA ANALYSIS

13.1 Analysis of Endpoints

13.1.1 Summary Statistics

The summary statistics produced from this exploratory study will be:

% participants successfully using the Apne-Scan DC1

Comparisons of primary diagnostic metric, AHI, between the standard sleep apnoea test device and Apne-Scan (based on recorded apnoeas and indicative hypopneas).

Primary Data Analysis

Comparison of primary diagnostic metric, AHI, between the standard sleep apnoea test device and Apne-Scan DC1.

Secondary Data Analysis

Comparison of primary diagnostic metric, AHI, segmented into mild, moderate and severe sleep apnoea, between the standard sleep apnoea test device and Apne-Scan DC1

Comparison of primary diagnostic metric, AHI, segmented into mild, moderate and severe hypopnoea, between the standard sleep apnoea test device and Apne-Scan DC1

Comparison of the participant's Apne-Scan data with their oxygen saturation levels from the standard test to identify the possibility of using the Apne-Scan data to predict the user's SPO2 level, possibly resulting in a first-generation algorithm, based on the Apne-Scan data, to predict the user's SPO2 level.

Analysis of the usability and effectiveness of the device in capturing the minimum data required for screening for sleep apnoea.

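### AHI is the only planned comparison of respiratory events with the standard device, so the study cannot show that Apne-Scan identifies the same apnoeas and hypopneas, as its title sets out to do

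*Combined protocol and SAP*

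**What the plan says.** The study title (section 3, Synopsis) describes an exploratory study of the device "to compare its capability to identify apnoeas and hypopneas" with that of standard test devices. Section 1.1 defines both terms as discrete events. An apnoea is a stop in breathing of more than 10 seconds. A hypopnoea is an airflow drop of at least 30% for more than 10 seconds with an oxygen fall of at least 3%.

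Section 13.1.1 gives the primary analysis as "Comparison of primary diagnostic metric, AHI, between the standard sleep apnoea test device and Apne-Scan DC1". The Apne-Scan AHI is "based on recorded apnoeas and indicative hypopneas". Two secondary analyses compare the devices on "AHI, segmented into mild, moderate and severe sleep apnoea" and on "AHI, segmented into mild, moderate and severe hypopnoea". The remaining items are the percentage of participants using the device successfully, the Apne-Scan signal against SPO2, and usability and data capture.

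Section 10.3.2.3 states a limit of the device: "The device will only recognise Indicative Hypopnea Events, because it does not confirm desaturation", unless its data prove able to predict SPO2.

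On data flow, section 1.6 says that the only standard-test data the company receives are oxygen saturation. Section 12.2 lists no scored reference events among the data collected. Section 10.3.1 has the clinical team compare the output of one device with the output of the other, without saying in what unit.

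**The concern.** Identifying events and agreeing on an hourly rate are different properties. A rate can agree while the two devices count different events. The protocol itself supplies one source of extra events, indicative hypopneas without a desaturation check, and any missed events would work in the opposite direction.

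The hypopnoea analysis has a further gap. It changes how participants are grouped, but the quantity compared is still AHI. An apnoea that Apne-Scan scores as a hypopnoea, or the reverse, leaves AHI unchanged and is invisible in all three comparisons.

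Close AHI agreement could therefore be reported, under the present title, as evidence that the device identifies apnoeas and hypopneas. Section 1.8 says the results will be used to develop an analysis program for clinicians, and section 9 says they will inform a larger powered study. Errors that happen to balance in this sample need not balance in another case mix.

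**Working it through.** The plan gives no figure to reproduce: section 9 sets 25 participants without a calculation, and no agreement statistic or margin is stated.

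**1. What AHI can identify.** Per hour, let T be events found by both devices, M reference events missed by Apne-Scan, and F Apne-Scan events with no reference counterpart.

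- Reference AHI = T + M; Apne-Scan AHI = T + F; difference = F − M.
- Event sensitivity = T/(T + M); PPV = T/(T + F).

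The AHI difference fixes F − M only. It carries no information on F and M separately.

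**2. Illustration (assumed rates).** Reference AHI 20/h, M = 6, F = 6, so T = 14.

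- Apne-Scan AHI = 14 + 6 = 20/h; difference 0.
- Sensitivity = 14/20 = 70%; PPV = 14/20 = 70%.

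**3. Balanced errors across 25 participants (simulation, 2,000 runs).** Assumptions, none from the documents: 6 h of recording; reference AHI lognormal with median 15/h and log-SD 0.9; severity cut-points 5, 15 and 30; each participant's false events equal on average to that participant's missed events. Mean bias was 0.00 in every row.

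| Event sensitivity | AHI correlation | Limits of agreement | Same severity category |
|---|---|---|---|
| 90% | 0.999 | ±1.6/h | 96% |
| 60% | 0.997 | ±3.0/h | 93% |
| 40% | 0.996 | ±3.4/h | 92% |

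When errors balance within participants, AHI agreement barely separates a good event detector from a poor one. The simulation assumes that balance and does not show it to be likely.

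**4. Unbalanced errors.** Keep 30% missed, but make false events a constant 6/h:

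- Reference 2/h: 0.7 × 2 + 6 = 7.4 (difference +5.4).
- Reference 20/h: 0.7 × 20 + 6 = 20 (difference 0).
- Reference 40/h: 0.7 × 40 + 6 = 34 (difference −6).

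Here the severity-stratified comparison would show a gradient. How much it reveals depends on whether false events rise with severity, which is unknown.

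**5. Precision of an event-level analysis.** Section 7.2.1 sets a minimum of 60 h of breathing data. At an assumed 15/h that is 60 × 15 = 900 reference events. For 70% sensitivity, half-width = 1.96 × √(0.7 × 0.3 ÷ (900/design effect)):

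- Design effect 5: effective n = 180, half-width 6.7 points.
- Design effect 10: effective n = 90, half-width 9.5 points.
- Design effect 20: effective n = 45, half-width 13.4 points.

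With 15 participants and 60 events each, a design effect of 10 corresponds to an intra-participant correlation of (10 − 1)/(60 − 1) ≈ 0.15. These figures pool both event types; separate intervals would be wider.

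**The case against.** The strongest reply is that the title is not the study objective. The primary hypothesis, the overall aim (6.1), the primary objective (6.2) and the safety hypothesis all concern the patient: supporting a diagnosis, recognising people without sleep apnoea, and not missing moderate or severe disease. Section 13.1.1 calls AHI the primary diagnostic metric, and for that purpose it is a fair choice. This stands. A reader might infer that AHI is the wrong primary analysis; the documents do not support that.

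A reader might also infer that AHI is the only analysis. It is not: section 13.1.1 also lists successful use, SPO2 and usability. None of these tests event identification, so the point holds only for comparisons of respiratory events. Nor do the documents say that the AHI covers the whole night; its time base is not stated.

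A third tempting reading is that errors will cancel. The documents give no missed-event rate. The one mechanism they describe, hypopneas without a desaturation check, acts in one direction and alone would raise the Apne-Scan AHI. Section 4.1 says that more than 25% of people referred are snorers; with few true events to miss, their false events would show as a positive difference. This partial safeguard is real, but limited. The listed strata are mild, moderate and severe, with none below mild, and 25 participants over three strata average about eight each.

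Two practical objections also stand. Section 10.3.2.3 describes sequential readings and mentions no clock, so time matching is not yet shown to be feasible, although the SPO2 objective has the same need. Hypopnoea PPV would also be lowered by definition, because the reference requires desaturation and Apne-Scan does not check it. The event analysis would partly restate a limit the protocol already discloses.

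**Conclusion.** The gap is between the title and the analysis. As planned, the study can describe AHI agreement, but it cannot show whether Apne-Scan finds the same apnoeas and hypopneas, or tells one from the other. This follows from the difference being F − M and needs no assumption about the data.

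The size is conditional. Zero AHI difference is compatible with 70% sensitivity and 70% PPV in the illustration, and with lower values if more errors balance. The documents give no basis for saying how much cancellation to expect, and the severity-stratified comparison would reveal only part of it. The half-widths of about 7 to 13 points rest on an assumed 15 events/h and assumed design effects of 5 to 20.

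The point does not undermine the primary analysis or the exploratory sample size. It is a worthwhile, low-cost addition, because both devices already record the same night.

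**What to change.** In section 13.1:

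1. Keep AHI as the primary analysis.
2. Report the apnoea index and the hypopnoea index separately for both devices, overall and within the planned severity groups.
3. As a secondary exploratory analysis, match the standard test's scored events (start, duration, type) in time to Apne-Scan's under an overlap rule set in advance. Report event sensitivity and PPV with participant-clustered intervals, separately for apnoeas and hypopneas. State that the missing desaturation check will lower hypopnoea PPV.
4. If exact matching is not workable, compare event counts in fixed 5-minute blocks. This is cruder: it does not give sensitivity or PPV, and errors can still cancel within a block.
5. If event data cannot be obtained, report the separate indices and limit the title and conclusions to AHI agreement.

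The cost is about 25 event-file exports, some extra analysis, a matching tolerance to set in advance, and a recorded clock alignment, which the SPO2 objective also needs. The data flow must also be settled. Either the clinical team, which already compares outputs under section 10.3.1, does the matching, or sections 1.6 and 12.2 are amended so that scored reference events can be shared. Section 14.2 governs any such amendment.

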4 BACKGROUND AND RATIONALE

4.1 Epidemiology

Sleep apnoea is a chronic condition where the person stops breathing for more than ten seconds (an apnoea) or shallow breathes for more than ten seconds (a hypopnea). Both events reduce the oxygenation of the blood. Less than 20% of sleep apnoea is caused by brain commands (central sleep apnoea) with more than 80% due to obstruction of the airways (obstructive sleep apnoea - OSA)¹.

OSA is a common, treatable condition. Recent research indicates that 936 million globally have mild-to-severe OSA, with 425 million with moderate-to-severe OSA¹. Even in first-world countries, the vast majority (up to 80%) of those affected remain undiagnosed and therefore untreated²⁻⁴. The lack of an appropriate level of case identification is driven by three factors: patients are frequently unaware of their own symptoms of sleep apnoea since they are often identified either by a bed partner or family member; clinicians in most medical specialties, and especially within primary care, do not have access to a simple sleep apnoea screening device; and health care professionals often lack the necessary training to identify high risk people and screen for early intervention. An accessible diagnostic technology and improved knowledge of the risk factors leading to sleep apnoea are therefore crucial to properly screen those with the highest risk.

1.5 million people in the UK have OSA. Up to 4 per cent of middle-aged men and 2 per cent of middle-aged women in the UK have OSA. It also affects 3 per cent of children in the general population; and as many as 50 per cent of children who are obese or have specific disabilities or other health conditions. Older people are even more at risk, with 15 to 20 per cent of those aged 70 and more estimated to have the condition. This means that OSA is the most common chronic respiratory condition, and the numbers affected are believed to be rising due to more people being overweight.⁴ Currently, due to the cost of the diagnostic equipment, OSA is diagnosed at specialist sleep clinics. More than 25% of the people referred to these centres are snorers, who could be screened out by Apne-Scan, releasing much needed specialist diagnostic capacity.

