6. AIMS AND OBJECTIVES

6.1 Overall Study Aim

The overall study aim of the study is an initial assessment of whether screening patients with possible sleep apnoea using Apne-Scan DC1 can support the clinician in reaching a diagnosis of sleep apnoea and whether Apne-Scan identifies people who do not have the symptoms of sleep apnoea.

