7.2 Outcome Measures

7.2.1 Research outcomes:

Primary Outcome

The primary outcome of interest is the data capture of the changing pressures in the user's breathing, whilst asleep, as recorded by the Apne-Scan DC1 device.

Note: The minimum evidence for successful completion of the study is 60 hours of breathing data captured by a minimum of 15 participants.

Secondary Outcomes

- An overall comparison of the OSA screening output from Apne-Scan DC1 with that from standard sleep apnoea test devices (ResMed NOX T3 and Phillips Alice Night One).
- A comparison stratified by the severity of the OSA indicated by standard sleep apnoea test devices.
- A comparison stratified by the severity of the hypopnoea indicated by standard sleep apnoea test devices.
- A possible first-generation algorithm, based on the Apne-Scan data, to predict the user's SPO2 level.

7.2.2 Safety Outcomes:

- Any adverse events (AEs) reported while performing the study procedures.
- Any adverse device effects (ADEs).

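### No prespecified analysis evaluates the rule-out half of the primary hypothesis or the safety hypothesis: neither device has a classification rule, reference-negative participants have no stratum, and missed moderate or severe cases are not counted

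*Combined protocol and SAP*

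**What the plan says.** **Hypotheses and aim.** The primary hypothesis in the Synopsis is that screening with the device "supports the clinician in reaching a diagnosis and identifies people who do not have the symptoms of sleep apnoea". Section 6.1 repeats the second half as part of the overall aim: "whether Apne-Scan identifies people who do not have the symptoms of sleep apnoea". The safety hypothesis is that "Apne-Scan DC1 does not indicate that users with moderate or severe sleep apnoea or hypopnea do not have the conditions".

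**Outcomes.** Section 7.2.1 opens: "The primary outcome of interest is the data capture of the changing pressures in the user's breathing". The secondary outcomes are an overall comparison of screening output with the standard devices, comparisons stratified by severity of sleep apnoea and of hypopnoea, and a possible SpO2 algorithm. Section 7.2.2 has two safety outcomes: "Any adverse events (AEs) reported while performing the study procedures", and adverse device effects.

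**Analysis.** The primary analysis in section 13.1.1 compares AHI between the two devices. The first secondary analysis is "Comparison of primary diagnostic metric, AHI, segmented into mild, moderate and severe sleep apnoea, between the standard sleep apnoea test device and Apne-Scan DC1". A parallel analysis covers hypopnoea, followed by SpO2 prediction and usability.

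**Expected population.** Section 4.1 says: "More than 25% of the people referred to these centres are snorers, who could be screened out by Apne-Scan".

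**The concern.** The rule-out claim and the safety claim each need every participant placed in a class by each device, followed by a count. For rule-out, the count is how many participants negative on the standard test Apne-Scan also calls negative. For safety, it is how many with moderate or severe disease on the standard test Apne-Scan calls negative. The plan asks for neither count and does not say what an Apne-Scan negative is.

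Two things are at stake. First, with the rule left open, a cut-off for an Apne-Scan negative could be picked once both sets of output are known, and that choice could decide the result. Second, in a study of 25 an informal statement that no moderate or severe case was missed could be taken as confirming the safety hypothesis, although the data would remain compatible with a substantial miss rate. Section 9 says the outcomes will inform the design of a powered study, and clearance and miss rates are natural inputs to that design.

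**Working it through.** **Step 1: set each claim against the plan.**

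| Claim | What it needs | What the plan provides |
|---|---|---|
| Rule-out half of the primary hypothesis (Synopsis; 6.1) | A reference-negative group, a rule for an Apne-Scan negative, the proportion cleared | An overall AHI comparison that includes these participants; strata that start at mild (6.3, 13.1.1); no rule; no proportion |
| Safety hypothesis (Synopsis) | A moderate/severe reference group, the same rule, a count of those cleared | Moderate and severe strata exist (13.1.1); no rule; no count; 7.2.2 covers AEs and ADEs only |

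The missing no-disease stratum bears on the first row only. The second row fails on the missing rule and count.

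**Step 2: can a negative be read off implicitly?** No AHI cut-off appears for either device. Section 1.1 defines a hypopnoea as including an oxygen fall of 3% or more. Section 10.3.2.3 says Apne-Scan recognises only indicative hypopnea events, because it does not confirm desaturation. The two AHIs therefore count different events, and a cut-off for one does not carry over to the other without justification.

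**Step 3: are the reference results listed as study data?** Section 12.2 lists baseline data, the questionnaire and the Apne-Scan recording. Section 1.6 sends the company only SpO2 from the standard test. Reference AHI and class are not listed, although section 10.3.1 has the clinical team comparing the two outputs, so that team holds them.

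**Step 4: likely group sizes.** Section 9 gives no calculation for 25, so there is no figure to reproduce. Section 10.5 sets a minimum of 15 participants.

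- Reference-negative, assuming that the snorers in 4.1 are reference-negative and taking 25% as the share: 0.25 × 25 = 6.25, about 6; 0.25 × 15 = 3.75, about 4.
- Moderate or severe, assuming that the global ratio in 4.1 (425/936 = 45.4%) applies to the remaining participants in this clinic: 18.75 × 0.454 = 8.5, so 8 or 9 of 25; 11.25 × 0.454 = 5.1, about 5 of 15. A referred population may well differ, so larger numbers are shown too.

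**Step 5: what perfect results would show.** For zero misses in n, the two-sided exact (Clopper-Pearson) 95% upper limit is 1 − 0.025^(1/n).

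| n moderate/severe (assumed) | Upper limit on miss rate |
|---|---|
| 5 | 52.2% |
| 8 | 36.9% |
| 9 | 33.6% |
| 10 | 30.8% |
| 12 | 26.5% |
| 15 | 21.8% |

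For n of n correctly cleared, the lower limit is 0.025^(1/n): 54.1% for 6/6 and 39.8% for 4/4.

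**Step 6: how often would zero misses occur by chance?** With a true miss rate of 10%, the probability is 0.9^n: 0.9^9 = 39% and 0.9^5 = 59%.

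**The case against.** The strongest reply is that the information is not lost. The overall AHI comparison in 13.1.1 and the overall comparison of screening output in 7.2.1 have no severity restriction, so participants without sleep apnoea are included. Under 10.3.1 the clinical team compares the Apne-Scan output with that of the standard device each participant used. A severe participant with a near-zero Apne-Scan AHI could show up in the severe stratum, especially in so small a study. This stands. A reader might infer that the study cannot bear on either hypothesis, or that its report would conceal a cleared severe patient. The documents do not support that, since 13.1.1 names no summary statistic and so does not confine the report to averages. What is missing is a prespecified rule and analysis.

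A second reply is that the study is declared exploratory (section 9), its aim is an initial assessment (6.1), its completion criterion is data capture (10.5), and participation does not alter NHS care (1.6). This also stands, and it limits what should be asked for: descriptive counts, not power. It does not explain stating two classification hypotheses and planning no analysis of them.

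A third reply is that the added table could not establish either hypothesis at this size. That is true, and the report should say so.

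**Conclusion.** The concern holds in this form: no prespecified analysis evaluates the rule-out half of the primary hypothesis or the safety hypothesis. The raw comparisons would contain relevant information, but the classification is open to choice after the data are seen, and zero misses is open to over-reading.

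Two wider readings should be avoided. A reader might infer that the absent no-disease stratum undermines both hypotheses; it affects only the rule-out claim, since moderate and severe disease do have strata. A reader might also infer that the whole primary hypothesis goes unassessed; the half about supporting the clinician's diagnosis is outside this point.

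On size, about 6 of 25 participants would have no stratum, if the snorers in 4.1 are reference-negative; because 4.1 says more than 25%, the expected number could be higher. Zero misses would leave upper limits of roughly 22% to 31% with 15 down to 10 moderate or severe cases. With the 8 or 9 cases implied by the global ratio the limits are about 37% and 34%, and with about 5 cases at the 15-participant minimum the limit is about 52%. All these denominators are assumptions; the documents do not give the expected severity mix for this clinic.

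**What to change.** 1. **Analysis.** In 13.1.1 and the matching outcome lists (Synopsis, 7.2.1), add a no-sleep-apnoea stratum and a descriptive cross-table of Apne-Scan class (none, mild, moderate, severe, no usable result) by reference class. Do this for sleep apnoea and, separately, for hypopnoea, because the safety hypothesis names both.
2. **Rule.** Fix the classification rule for each device before outputs are compared, with a justification that recognises that Apne-Scan counts indicative hypopneas without confirmed desaturation. Say explicitly that reference-negative status stands in for the absence of symptoms named in the primary hypothesis.
3. **Data.** Add the reference AHI and class, held by the clinical team, to section 12.2.
4. **Reporting.** Give, with exact 95% intervals, the proportion of reference-negative participants cleared and the proportion of reference moderate or severe participants cleared. Name the second as the outcome for the safety hypothesis.
5. **Interpretation.** State that zero misses at this size does not establish the safety hypothesis, and that the figures feed the planned powered study.

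Alternatively, move both hypotheses to that study and remove them from this one.

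The cost is one extra table (produced for both conditions), agreement on the rules in advance, a small data item passed from the clinical team, and a more modest safety claim.
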